9.6. Criteria for Disease Control

Disease control definition among measurable and non-measurable disease combination

Controlled Disease	Non-measurable disease (i.e., bone)	Measurable disease (i.e., lung, liver, lymph nodes)
Type I measurable disease only	None	CR or PR, or SD \geq 4 months or no true PD (at cycle10)
Type II non-measurable disease only	CR, or SD \geq 4 M	None
Type III Both measurable and non-measurable disease	CR, or SD \geq 4 M	CR or PR, or SD \geq 4 months or no true PD (at cycle10)

A patient with PD of measurable disease prior to end of cycle 10 would be considered to have disease control if the PD is not confirmed at the end of cycle 10.

9.7. Response will not be considered evaluable in the following categories:

9.7.1. Early Deaths: Patients who die within the first 2 weeks of the initiation of drug therapy owing to concurrent disease. These cases will be considered treatment failures in the intent-to-treat analysis.

9.7.2. Lost to Follow-up: Patients for whom there is inadequate information to judge tumor response because of loss of contact with our institution (>2 months after a missed appointment) and with referring physician in spite of repeated attempts to locate them. These cases will be considered treatment failures in the intent-to-treat analysis.

9.7.3. Major Protocol Violation: Patients who significantly deviate from the treatment program by either adding or deleting another agent or another therapeutic maneuver or by modifying substantially the dosage and schedule of the drug under evaluation. Patients who do not fulfill the requirements outlined under Patient Eligibility are also included in this category.

9.8. Down staging is defined as a change in the tumor extent that results in reclassification of the primary tumor and/or regional lymph node metastases into a different (lower) T, N, or M subgroup.

9.9. All subjective toxic effects encountered during the study will be evaluated according to the CTCAE version 4.0. Objective toxic effects will be considered as the maximum numerical deviation from the normal range.

9.10. The survival of patients will be measured from the date of registration.

9.11. Patients will be monitored for 1 year after removal from the study or until death, whichever occurs first. Patients removed from study for unexpected adverse events will be monitored until AE is resolved or stabilized.

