13.0. Statistical consideration

13.1. Statistical design

The primary objective of this phase II trial is to assess the efficacy of talimogene laherparepvec as a single agent in locally recurrent IBC and non-IBC patients. The primary endpoint is the rate of overall response.

The overall response rate is defined as the percentage of CR, PR in overall patients. Patients will be evaluated for disease control at the end of cycle 4 (2 months), cycle 8 (4 months) and cycle 10 (5 months). If patients have measurable disease only and achieve CR or PR, they will be considered Response Type I. If patients have non-measurable disease only, and achieved CR, they will be considered as Response Type II. If patients have both measurable and non-measurable disease and achieve CR or PR at the measurable disease sites, and achieved CR at the non-measurable disease site, they will be considered as Response Type III. If patients have mixed responses such as progression of measurable disease and no progression of non-measurable disease at 5 months or vice versa, they will be considered to have uncontrolled disease. The Overall Response rate will be defined as a sum of the 3 response types.

The trial will be conducted using a two-stage design and the overall response rate will be estimated accordingly. It is assumed that the talimogene laherparepvec single agent will have a response rate of 20%. A response rate of 5% or lower will be considered treatment failure and the regimen will be rejected under this circumstance. 13 patients will be enrolled to the first stage. The study accrual will be delayed until all 13 patients are evaluable for response. A summary report will be submitted to the medical monitor in the IND office. If no patients achieve an overall response to the treatment, the trial will be stopped and the regimen will be declared as ineffective. If there are 1 or more patients achieve an overall response, 22 more patients will be enrolled to the study to reach a total of 35 treated patients. By the end of the study, the new regimen will be rejected if less than or equal to 3/35 patients achieve overall response and will not be considered worthy of further investigation otherwise.

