We have reviewed the 8 patients treated thus far, and determined that 1 of those 8 patients would not be eligible per the current proposed revised criteria due to extensive ($\geq 5\%$ Total Body Surface) skin lesion and will be replaced. As such, the overall sample size will be increased to 36 by one more patient. The afore mentioned one patient that is still evaluable for toxicity and efficacy in the overall end analysis, but not as a part of the evaluation for the 13 patients treated in the first stage. The above two-stage design statistical analysis plan will not change.

The operating characteristics of the trial are given as follows. When the true response rate is 5% the probability of stopping the trial early is 51% and the probability of claiming the regimen to be promising is 8.4%. On the other hand, if the response rate is 20%, the probability to stop the trial early is 5% and the probability of claiming the regimen to be promising is 90%. The

expected sample sizes are 23.7 and 33.8 when the true overall response rates are 5% and 20%, respectively

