Secondary objectives includes determining the overall disease control rate, local overall response rate and disease control rate, PFS, and OS in all patients; the local overall response rate and disease control rate, PFS, and OS in patients without distant metastases; and the local overall response rate and disease control rate, PFS, and OS in patients with distant metastases for defining the local efficacy of talimogene laherparepvec injection among breast cancer patients with inoperable local recurrence after surgery. In addition, this includes safety and tolerability of talimogene laherparepvec in these patients. The definition of PFS is time from treatment initiation until disease progression or death and this progression needs to be confirmed after the end of cycle 10. For example, patients who showed progress at 2 months but responded as PR at 5 months, we determine this as PR. In contrast, patients who showed progress at 2 months and was confirmed PD at 5 months, we determine this as PD at 2 months. The definition of OS is time from treatment initiation until any cause of death.

Analysis plan:

By the end of the study, the overall response rate will be estimated with 95% confidence intervals for all evaluable patients and for patients with or without distant metastasis, separately. PFS and OS from registration will also be estimated using Kaplan-Meier method with 95% confidence intervals.

Biomarker endpoints will be measured in tissue and in surrogate blood or plasma before and after the treatment. Correlation between biomarkers from various markers and between tissue and blood/plasma will be assessed by Pearson or Spearman rank correlation coefficients for

continuous biomarkers and by chi-square or Fisher's exact test for discrete covariates. The associations between markers or change in the level of markers and overall response status will first be assessed graphically and then tested using a t-test/analysis of variance or Wilcoxon rank sum test/Kruskal-Wallis test, when appropriate. Repeated measures analysis including mixed effects modeling will be performed to analyze biomarkers change over time. We may also evaluate the association between the changes in the level of marker and the overall response status.

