13.2 Primary endpoint

The rate of overall response for measurable and immeasurable disease in all patients.

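### The analysis plan estimates the primary response rate in evaluable patients, although the endpoint is defined in all patients, and Section 9.7.3 makes protocol violators not evaluable without counting them as failures

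*Combined protocol and SAP*

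**What the plan says.** Section 9.7 lists three groups whose response is not evaluable. For early deaths (9.7.1) and losses to follow-up (9.7.2) it adds: "These cases will be considered treatment failures in the intent-to-treat analysis". The third group, major protocol violation (9.7.3), covers "Patients who significantly deviate from the treatment program by either adding or deleting another agent or another therapeutic maneuver", as well as substantial changes to dose or schedule. It also takes in ineligible patients: "Patients who do not fulfill the requirements outlined under Patient Eligibility are also included in this category". No failure sentence follows.

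The population for the primary rate is stated in three places:

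- Section 13.1, definition: "The overall response rate is defined as the percentage of CR, PR in overall patients".
- Section 13.2, primary endpoint: "The rate of overall response for measurable and immeasurable disease in all patients".
- Section 13.1, analysis plan: "the overall response rate will be estimated with 95% confidence intervals for all evaluable patients".

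The decision rule in Section 13.1 is a count: "the new regimen will be rejected if less than or equal to 3/35 patients achieve overall response". The same section raises the sample size to 36 to replace a patient who does not meet the revised skin criterion. That patient is described as "one patient that is still evaluable for toxicity and efficacy in the overall end analysis", but is not part of stage 1.

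**The concern.** The first two statements of the population agree with each other and the third does not. Section 13 does not define evaluable, so the only available definition is Section 9.7. On that reading the reported rate and interval leave out all the 9.7.3 patients. They also leave out early deaths and losses to follow-up, because those count as failures only in an intent-to-treat analysis that Section 13 never specifies.

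Membership of the 9.7.3 group is decided after treatment starts. The thresholds for a significant deviation or a substantial modification are not given. Adding an agent or departing from the schedule is often related to how the disease is doing, so the exclusion need not be neutral. The trial has a single arm, and the response rate with its interval is its main reported result. Two analysts could follow this plan correctly and report different denominators.

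**Working it through.** **Inputs.** From Section 13.1: stage 1 of 13 patients, stop at 0 responses; 22 more patients to reach 35; reject at 3 or fewer responses; failure rate 5%, target rate 20%. The number of 9.7.3 patients is not in the documents. A range of 1 to 5 is assumed below.

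**1. The plan's own figures.** With p the true response rate:

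- P(stop early) = (1 − p)^13
- P(promising) = Σ over x = 1 to 13 of Binom(x; 13, p) × P(at least 4 − x responses in 22)
- Expected N = 13 + 22 × [1 − P(stop early)]

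| | p = 5% | p = 20% |
|---|---|---|
| Early stop, computed (stated) | 51.3% (51%) | 5.5% (5%) |
| Promising, computed (stated) | 8.44% (8.4%) | 90.3% (90%) |
| Expected N, computed (stated) | 23.7 (23.7) | 33.8 (33.8) |

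The design figures are sound and are not at issue.

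**2. Effect on the reported rate.** Exact (Clopper-Pearson) 95% intervals, which are an assumption because the plan names no interval method:

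| Case | Rate | 95% CI |
|---|---|---|
| 4 of 35, nobody dropped | 11.4% | 3.2 to 26.7 |
| One non-responder dropped, 4/34 | 11.8% | 3.3 to 27.5 |
| Five non-responders dropped, 4/30 | 13.3% | 3.8 to 30.7 |
| 4 of 36, nobody dropped | 11.1% | 3.1 to 26.1 |
| Five non-responders dropped, 4/31 | 12.9% | 3.6 to 29.8 |

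Dropping five non-responders moves the rate by 13.3 − 11.4 = 1.9 points on 35 patients, and by 12.9 − 11.1 = 1.8 points on 36.

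The opposite direction is also possible. If 5 of 35 respond (14.3%) and one responder is classed under 9.7.3, the result is 4/34 = 11.8%.

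**3. Effect on the decision.** The rule counts responders, and removing non-responders leaves that count as it was.

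**4. Denominator 35 or 36.** If the cut-off of 4 responses were applied to 36 patients, with the extra one added after stage 1 (13 + 23), the same formula gives P(promising) = 9.04% at a true 5% and 90.9% at a true 20%. The stated 8.4% holds only on 35.

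**The case against.** The authors may have intended an intent-to-treat analysis. Section 9.7 names one twice, and an evaluable-patient rate can stand beside it. Deaths and losses need a failure sentence because no response is observed, whereas a violator usually has one. Section 13.1 also uses evaluable loosely, since it applies the word to a patient who fails the revised criteria. This is a fair account of intent, but it does not settle which rate is primary, because the analysis plan mentions only the evaluable one.

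The 9.7.3 group may be small. Section 6.4 already treats the need for a new anticancer agent as a reason to stop treatment, Section 6.3.3 regulates delays, and Sections 6.3.3 and 8.0 allow background therapy. That limits the size of the problem. It does not say how those who remain are counted.

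The handling of the replaced patient is largely settled in Section 13.1. What is missing is the resulting denominator in the analysis plan.

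Three stronger readings are tempting:

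- **The go/no-go decision is biased toward success.** It is not. Dropping non-responders leaves the count unchanged, and dropping a responder could only lower it.
- **The exclusion can lift the interval above the 5% failure rate.** The lower limit is 4.7% for 5/36 and 5.1% for 5/33. With up to five non-responders dropped, however, this crossing happens only at exactly 5 responders. At 3 or 4 the limit stays at or below 3.8%, and at 6 or more it is at least 6.4% throughout. The plan attaches no decision to the interval.
- **Responses seen after surgery or permitted radiation must be disallowed.** Sections 3.0 and 5.1.4 foresee both. Scoring as a non-responder a patient whom treatment made operable would be a debatable choice, and the 4-week phrase in 9.1 and 9.2 need not mean that a response must be held that long.

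**Conclusion.** The point holds as an inconsistency in the primary analysis population. As written, the analysis plan departs from the endpoint definition and allows exclusion after baseline on an undefined judgement, with no scoring rule for 9.7.3 patients. The bias in the reported rate is upward if those dropped are non-responders and downward if they are responders. In the examples above with 4 responders and up to five non-responders dropped, it is about 2 points at most, inside an interval about 23 points wide. That size rests on the assumed number dropped and on exact intervals. The two-stage operating characteristics are correct, and the 3/35 decision is unaffected by dropping non-responders. The matter should be corrected because it concerns the main reported estimate and costs little, not because it threatens the trial's conclusion.

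**What to change.** 1. **Analysis plan, Section 13.1.** Estimate the overall response rate and its 95% interval in all treated patients, in line with the definitions in Sections 13.1 and 13.2. Report the evaluable-patient rate only as a sensitivity analysis.
2. **Section 9.7.3.** Count a treatment deviator with no response documented before the deviation as a non-responder. Classify ineligible patients by their observed response, as Section 13.1 already does for the replaced patient.
3. **Analysis plan, Section 13.1.** State that the replaced patient enters the overall estimate (denominator 36), while the 3/35 rule is applied to the 35 design patients.

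The cost is wording in two places. Sample size, stage 1 rule and cut-off stay as they are. The reported response rate may be slightly lower. Counting deviators as non-responders can also reduce the chance of a positive result. As an upper bound, if 5%, 10% or 15% of patients (assumed) were deviators who all counted as failures, independently of their true response, replacing p by p × (1 − share) in the formula above gives power at a true 20% of about 88%, 85% or 82%. Type I error at a true 5% would fall to 7.3%, 6.2% or 5.3%.

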10.0. Investigational drug management

10.1. Prescription

Talimogene laherparepvec will be provided by Amgen Inc. and dispensed by the investigational pharmacy at MD Anderson.

10.2. Treatment compliance

The study drug must be dispensed only by an appropriately qualified person to patients in the study. The drug is to be used in accordance with the protocol by patients who are under the direct supervision of an investigator.

10.3. Packaging and labeling

Talimogene laherparepvec medication labels will comply with legal requirements.

10.4. Storage and accountability

Talimogene laherparepvec will be supplied to the pharmacy of the investigational site/institution by Amgen Inc. Talimogene laherparepvec should be stored away from light and according to the storage and expiration information (where required) provided on the label that is affixed to the package containing the investigational product. See detailed information in Appendices section 15.7 and/or the package insert in Appendix P in PDOL

The study drug must be stored in a secure area with limited access. It will be administered only to patients entered into the clinical study, at no cost to the patients, in accordance with the conditions specified in this protocol.

The investigational pharmacy will maintain accurate records of the dates and amounts of shipments of the study drug, recipients of the drug (patient-by-patient accounting), and any study treatment accidentally or deliberately destroyed. At the end of the study, the amount of study drug supplied, dispensed, and subsequently destroyed or returned to MD Anderson's investigational pharmacy must be reconciled. Used or expired study drug will be disposed per MD Anderson Cancer Center policy.

11.0. Safety monitoring and reporting

11.1. Adverse events

AEs will be assessed according to the CTCAE version 4.0 before each cycle. All study participants who have received any dose of talimogene laherparepvec will be evaluable for safety. Unexpected adverse events including laboratory adverse events deemed clinically significant by the investigator will be graded and recorded.

An AE is an undesirable medical occurrence (sign, symptom, or diagnosis) or worsening of a pre-existing medical condition (e.g., diabetes, congestive heart failure, rheumatoid arthritis) that occurs after the initiation of the investigational product, regardless of whether it is considered to be related to the investigational product. The worsening of an existing medical condition occurs when a condition that was present at baseline (e.g., cancer, diabetes, migraine headaches, gout) becomes more severe, more frequent, or increased in duration during treatment with the investigational product. Grade 2 or higher non-hematologic AEs and grade 3 or higher hematologic AEs will be recorded upon observation by the investigator or reported by the patient (regardless of whether they are attributed to investigational product), documented in the patient's medical record, and recorded in CORe. Grade 2 or higher abnormal lab values will be recorded as AEs; and grade 1 abnormal laboratory values will not be recorded as AEs, however, any clinical consequences of the abnormality and related grade 1 abnormality should be recorded as AEs. Hospitalization for elective surgery or routine clinical procedures that are not the result of an AE (e.g., surgical insertion of a central line) need not be considered AEs and should not be recorded as an AE. Disease progression should not be recorded as AEs. The Investigator is responsible for verifying and providing source documentation for all adverse events and assigning attribution for each event for all subjects enrolled on the trial.

11.2. Serious adverse event (SAE) reporting

An adverse event or suspected adverse reaction is considered “serious” if, in the view of either the investigator or the sponsor, it results in any of the following outcomes:

- Death
- A life-threatening adverse drug experience – any adverse experience that places the patient, in the view of the initial reporter, at immediate risk of death from the adverse experience as it occurred. It does not include an adverse experience that, had it occurred in a more severe form, might have caused death.
- Inpatient hospitalization or prolongation of existing hospitalization
- A persistent or significant incapacity or substantial disruption of the ability to conduct normal life functions.
- A congenital anomaly/birth defect.

Important medical events that may not result in death, be life-threatening, or require hospitalization may be considered a serious adverse drug experience when, based upon appropriate medical judgment, they may jeopardize the patient or subject and may require medical or surgical intervention to prevent one of the outcomes listed in this definition.

Examples of such medical events include allergic bronchospasm requiring intensive treatment in an emergency room or at home, blood dyscrasias or convulsions that do not result in inpatient hospitalization, or the development of drug dependency or drug abuse (21 CFR 312.32).

- Important medical events as defined above, may also be considered serious adverse events. Any important medical event can and should be reported as an SAE if deemed appropriate by the Principal Investigator or the IND Sponsor, IND Office.
- All events occurring during the conduct of a protocol and meeting the definition of a SAE must be reported to the IRB in accordance with the timeframes and procedures outlined in “The University of Texas M. D. Anderson Cancer Center Institutional Review Board Policy for Investigators on Reporting Serious Unanticipated Adverse Events for Drugs and Devices”. Unless stated otherwise in the protocol, all SAEs, expected or unexpected, must be reported to the IND Office, regardless of attribution (within 5 working days of knowledge of the event).
- **All life-threatening or fatal events**, that are unexpected, and related to the study drug, must have a written report submitted within **24 hours** (next working day) of knowledge of the event to the Safety Project Manager in the IND Office.
- Unless otherwise noted, the electronic SAE application (eSAE) will be utilized for safety reporting to the IND Office and MDACC IRB.
- Serious adverse events will be captured from the time of the first protocol-specific intervention, until 30 days after the last dose of drug, unless the participant withdraws consent. Serious adverse events must be followed until clinical recovery is complete and laboratory tests have returned to baseline, progression of the event has stabilized, or there has been acceptable resolution of the event.

- Additionally, any serious adverse events that occur after the 30 day time period that are related to the study treatment must be reported to the IND Office. This may include the development of a secondary malignancy.
- The gene therapy reporting addendum (“Additional Reporting Form for Serious Adverse Events on Gene Transfer Trials”) must be included with each SAE submitted.

Reporting to FDA:

- Serious adverse events will be forwarded to FDA by the IND Sponsor (Safety Project Manager IND Office) according to 21 CFR 312.32.

It is the responsibility of the PI and the research team to ensure serious adverse events are reported according to the Code of Federal Regulations, Good Clinical Practices, the protocol guidelines, the sponsor’s guidelines, and Institutional Review Board policy.

